### Assessments during procedure:

### At the start of CPB:

- Blood product transfusions;
- Record CytoSorb start time;
- Operational notes (surgery/CPB start time, clamp times);
- Flow rate in CytoSorb circuit;
- Adverse events;
- Administration of fluids will be collected;
- Supplementation with Calcium or Albumin will be recorded;
- Concomitant medications will be collected, as needed;
- FiO2
- Blood samples will be drawn for the following assessments:
  - ABG;
  - Ionized calcium;

- Total serum calcium;
- Serum albumin;
- ACT (per SOC);
- Complement C3a and C5a;
- Inflammatory mediator panel;
- Plasma free hemoglobin (pfHb);

### Hourly while on CPB:

- Vasopressor requirements;
- Administration of fluids will be collected;
- Supplementation with Calcium or Albumin will be recorded;
- Flow rate in CytoSorb circuit (record flow rates every 30 minutes during treatment with CytoSorb device(s));
- Blood product transfusions;
- Blood samples will be drawn for the following assessments:
  - ABG;
  - Ionized calcium;
  - Total serum calcium;
  - Serum albumin;
  - ACT (per SOC);
  - Complement C3a and C5a;
  - Inflammatory mediators;
  - Plasma free hemoglobin (pfHb);

### 90 minutes from start of CPB:

- Record the start time of the second CytoSorb device and stop time;
- Blood samples will be drawn for the following assessments:
  - Complement C3a and C5a;
  - Inflammatory mediators;
  - Plasma free hemoglobin (pfHb);

### End of CPB (i.e. pump shut off, prior to protamine):

• Vital signs;

- Vasopressor requirements;
- Administration of fluids will be collected;
- Supplementation with Calcium or Albumin will be recorded;
- Record the stop time of the CytoSorb device(s);
- Blood product transfusions;
- Record type of surgical procedure(s);
- Operational notes (surgery/CPB stop time, clamp times);
- Urine output;
- Adverse events;
- Concomitant medications will be collected as needed;
- FiO2
- Blood samples will be drawn for the following assessments:
  - Hematology;
  - Coagulation panel;
  - Comprehensive metabolic panel;
  - ABG;
  - Ionized calcium;
  - ACT (per SOC);
  - Serum creatinine;
  - Complement C3a and C5a ;
  - Inflammatory mediator panel;
  - Plasma free hemoglobin (pfHb);

### 8.5.3.2 Control Arm

Subjects randomized to the control arm will receive standard of care bypass at the beginning of CPB.

The following procedures will be performed, and results recorded in the eCRF:

• Eligibility based on inclusion / exclusion criteria will be confirmed. Subjects who meet all inclusion and exclusion criteria will be randomized to either the control arm or to the treatment arm

- Vital signs
- Sequential Organ Failure Assessment (SOFA) score will be assessed before induction of anesthesia;
- Initiate recording of fluids administration (e.g. crystalloids)
- Initiate recording of supplementation with calcium and/or albumin
- Blood samples will be drawn for the following assessments:
  - Hematology
  - Coagulation panel
  - Comprehensive metabolic panel
  - o ABG
  - Ionized Calcium
  - ACT (per SOC)
  - Serum creatinine
  - Complement C3a and C5a
  - Inflammatory mediator panel
  - Kidney injury markers urine: urine NGAL, IGFBP7, TIMP2);
  - Kidney injury markers plasma: HMGB1 and Cystatin C;
  - Plasma free hemoglobin (pfHb);

### Assessments during procedure:

### At the start of CPB:

- Blood product transfusions
- Operational notes (surgery/CPB start time, clamp times)
- Administration of fluids will be collected
- Supplementation with Calcium or Albumin will be recorded
- Adverse events
- Concomitant medications will be collected as needed
- FiO2
- Blood samples will be drawn for the following assessments:
  - o ABG

- Ionized calcium
- Total serum calcium
- Serum albumin
- ACT (per SOC)
- Complement C3a and C5a
- Inflammatory mediator panel
- Plasma free hemoglobin (pfHb)

### Hourly while on CPB:

- Vasopressor requirements
- Administration of fluids will be collected
- Supplementation with Calcium or Albumin will be recorded
- Blood product transfusions
- Blood samples will be drawn for the following assessments:
  - o ABG
  - Ionized calcium
  - Total serum calcium
  - Serum albumin
  - ACT (per SOC)
  - Complement C3a and C5a
  - Inflammatory mediator panels
  - Plasma free hemoglobin (pfHb)

### 90 minutes from start of CPB:

- Blood samples will be drawn for the following assessments:
  - Complement C3a and C5a
  - Inflammatory mediator panels
  - Plasma free hemoglobin (pfHb)

### **End of CPB** (i.e. pump shut off, prior to protamine):

• Vital signs

- Vasopressor requirements
- Administration of fluids will be collected
- Supplementation with Calcium or Albumin will be recorded
- Blood product transfusions
- Record type of surgical procedure(s)
- Operational notes (surgery/CPB stop time, clamp times)
- Urine output
- Adverse events
- Concomitant medications will be collected as needed
- FiO2
- Blood samples will be drawn for the following assessments:
  - Hematology
  - Coagulation panel
  - Comprehensive metabolic panel
  - o ABG
  - Ionized Calcium
  - ACT (per SOC)
  - Serum creatinine
  - o Complement C3a and C5a
  - Inflammatory mediator panels
  - Plasma free hemoglobin (pfHb)

## 8.5.4 Sampling during CPB

Subject blood samples to be drawn from an arterial line during CPB procedure by appropriate medical staff per institutional guidance (i.e., anesthesiologist or perfusionist).

## 8.5.5 Sampling End of CPB (i.e. pump shut off, post protamine)

Subject blood samples will be drawn by appropriate medical staff (i.e. anesthesiologist or perfusionist) per institutional guidelines, post-cardiac surgery. Note that samples for hematology and coagulation assessments should be drawn after the administration of protamine at a timepoint consistent with the standard of care for the institution.

### 8.5.6 Sample Collection and Storage

Instructions on the process for the collection and storage of the blood and urine samples are provided in the Study Laboratory Manual.

### 8.6 Post-Surgical Care Unit (i.e., CCU, ICU)

Admission to Post-Surgical Care Unit through 7 days or hospital discharge, whichever occurs first

### 8.6.1 Admission to Post-Surgical Care Unit (Treatment and Control Groups)

The following assessments will be performed within one hour after admission to the postsurgical care unit.

- Vital signs
- Weight
- FiO2 (if the patient is intubated on mechanical ventilatory support)
- SOFA Score
- Record vasopressor requirements
- Blood product transfusions
- Record need for ventilation and mechanical support
- Record need for renal replacement
- Record urine output each hour for the first 48 h after surgery even if catheter is removed before 48 h
- Adverse events
- Concomitant medications will be collected as needed
- Administration of fluids will be collected
- Supplementation with Calcium or Albumin will be recorded
- Blood samples will be drawn for the following assessments:
  - $\circ$  Hematology
  - Coagulation panel
  - Comprehensive metabolic panel
  - ABG (per SOC)
  - Ionized calcium
  - ACT (per SOC)

- Serum creatinine
- Complement C3a and C5a
- Inflammatory mediator panel Kidney injury markers (plasma): HMGB1, Cystatin
   C:
- Kidney injury markers (urine): NGAL, IGFBP7, TIMP2);
- Plasma free hemoglobin (pfHb)

### 8.6.2 Post-Surgical Days 1-3

- Vital signs
- Weight
- FiO2 (if the patient is intubated on mechanical ventilatory support)
- SOFA Score
- Record vasopressor requirements
- Blood product transfusions
- Record need for ventilation and mechanical support
- Record need for renal replacement
- Record urine output each hour for the first 48 h after surgery even if the catheter is removed before 48 h
- Adverse events
- Concomitant medications will be collected as needed
- Administration of fluids will be collected (Day 1 only required, SOC thereafter)
- Supplementation with Calcium or Albumin will be recorded (Day 1 only required, SOC thereafter)
- Blood samples will be drawn for the following assessments:
  - Hematology
  - Coagulation panel (per SOC)
  - Comprehensive metabolic panel
  - Serum creatinine
  - Complement C3a and C5a
  - ABG (per SOC)

- Ionized Calcium
- Inflammatory mediator panel
- Kidney injury markers (plasma): HMGB1, Cystatin C
- Kidney injury markers (urine): NGAL, TIMP2, IGFBP7)

### 8.6.3 Post-Surgical Day 4 through 7

### (or hospital discharge, whichever occurs first) (Treatment and Control Groups)

The following assessments will be performed daily starting on post-surgical day 4 through day 7, or until hospital discharge, whichever occurs first:

- Vital signs
- Weight
- FiO2 (if the patient is intubated on mechanical ventilatory support)
- Record vasopressor requirements
- Blood product transfusions
- Record need for ventilation and mechanical support
- Record need for renal replacement
- Record urine output
- Adverse events
- Concomitant medications will be collected as needed
- Administration of fluids will be collected
- Supplementation with Calcium or Albumin will be recorded
- Blood samples will be drawn for the following assessments:
  - Hematology (per SOC)
  - Coagulation panel (per SOC)
  - Comprehensive metabolic panel (per SOC)
  - Serum creatinine

### 8.6.4 Hospital Discharge

The following information with be collected at the time of hospital discharge:

• SOFA Score

- Record need for ventilation and mechanical support
- Record need for renal replacement
- Record urine output
- Hospital discharge date (to calculate duration of hospital stay)
- Adverse events
- Contact information where subject is going if less than 7 days post-cardiac surgery
- Pertinent concomitant medications
- Hematology
- Coagulation panel
- Comprehensive Metabolic Panel
- Serum Creatinine

### 8.7 Day 30 Post-Cardiac Surgery

The subjects will be contacted via telephone at 30 days post-cardiac surgery for assessment of the following since hospital discharge:

- Blood product transfusions
- Adverse events

### Table 3: Schedule of Assessments

		1	Procedure (CP	B/Surgery)			Post-Surgery period	Discharge	Follow-up	
Event	Screening 	Pre-Procedure (before induction of general anesthesia)	Start of CPB (±5 minutes)	Hourly while on CPB (±5 minutes)	End CPB (post protamine)	Admission to Post- Surgery Care unit (+1 hour)	Daily for Post day 1-3 Post-Cardiac Surgery or Hospital Discharge (whichever is sooner) 	Day 4-7 Post- Cardiac Surgery	Hospital Discharge	30 Day Follow-up (±5 days)
Informed Consent	Х									
Demographics, Height	X									
Weight	X	Х				X	Х	Х		
Medical History	X									
Prior Medications (taken within 60 days of Screening Visit)	X									
Concomitant Medications – inclusive of IV contrast media administered within 48 h of procedure			As Needed							
Inclusion/Exclusion Criteria (w/in 14 days of surgery)	X									
Inclusion/Exclusion Review		Х								
Vital Signs (HR, BP, Temp) 	X	Х			Х	X	Х	Х		
New York Heart Association (NYHA)	X									
Echocardiogram (Ejection Fraction) 	X									
Estimated Glomerular Filtration Rate (eGFR)	X									
Physical Examination	X									
SOFA Score (includes FiO2, level of hypotension assessment, evaluation of		X 				X 	X 		X 	

		Procedure (CPB/Surgery)					Post-Surgery period	Discharge	Follow-up	
Event	Screening 	Pre-Procedure (before induction of general anesthesia)	Start of CPB (±5 minutes)	Hourly while on CPB (±5 minutes)	End CPB (post protamine)	Admission to Post- Surgery Care unit (+1 hour)	Daily for Post day 1-3 Post-Cardiac Surgery or Hospital Discharge (whichever is sooner) 	Day 4-7 Post- Cardiac Surgery	Hospital Discharge	30 Day Follow-up (±5 days)
mechanical ventilation and vasopressor requirement, MAP, Glasgow Coma Score) 										
Randomization		$X^4$								
Vasopressor Requirements 				Х	Х	X	X	Х	X9	
FiO 2 (if patient is intubated on mechanical ventilatory support)		X	Х		X	X	X	Х		
Start/Stop Times of CytoSorb Treatment & Flow rate every 30 minutes (Treatment arm only)			X	X	Х					
Blood Product Transfusions 			Х	Х	Х	X	X	Х	X	Х
Ventilation & Mechanical support Requirements						X	X	Х	X	
Renal Replacement Requirements						X	X	Х	X	
Type of Surgical Procedure(s)					Х					
Administration of fluids is recorded 		X						X		
Supplementation with Ca and/or Albumin 		X						X		
Operational notes (Surgery start & stop times, clamp times)			Х		X					
Adverse Events/SAEs			As	Needed (from	time ICF is	signed and su	bject is enrolled until s	study exit)		

 Within 14 days of surgery. If Screening is completed on the day of surgery, duplicate pre-procedure assessments/procedures do not need to be repeated.

 Daily, preferably at the same time each day.

 After approximately 5 minutes supine

 Randomization can be performed within 5 days prior to the cardiac surgery, but only after informed consent has been obtained.

 A minimum of 12 hours from time of admission to Post-Surgery Care Unit to the start of collection of data for daily is required.

 Echocardiogram for ejection fraction if an acceptable method (Section 6.4.1, Inclusion 3d) has not been completed within 90 days.

SOFA score will be assessed pre-procedure (before induction of anesthesia or sedation); on admission to post-surgical care; daily for 3 days post-procedure; and at Day 7 post-procedure or discharge, whichever occurs first). For post-surgical SOFA assessments, the lowest mean arterial pressure (MAP) from the day is used in the SOFA determination.

Vasopressor requirements: the maximum vasopressor dosage will be recorded each day (maximum dose over 1 hour).

 Vasopressors will be collected through day 7 if subject is still hospitalized.

 Blood transfusions will be collected through 30 days post cardiac surgery. Transfusion type (e.g. whole blood, packed red cells, platelets) will be recorded along with the volume administered

 Administration of fluids (crystalline) and supplementation with calcium and/or albumin begins at pre-procedure and will continue through the end of post-surgical Day 1. All administration and supplementation will be recorded. Following Day 1, administration of fluids and supplementation will be recorded as SOC until the point where the treating physician discontinues collection.

		Procedure (CPB/Surgery)						t-surgical pe	Discharge	Follow Up	
Event	Screening 	Pre-procedure Day of surgery but before induction of anesthesia	Start of CPB (±5 min)	Hourly while on CPB (±5 min)	90 minutes after Start of CBP Start of Device # 2) (±5 min)	End CPB  Off pump and post protamine	Admission to post- surgical care unit (+ 1 h)	Post- surgical Days 1-3	Post- surgical Days 4-7 or discharge, whichever is sooner	Hospital Discharge	30-day Follow up (±5 days)
Pregnancy Test 	Х										
Hematology 	X	X 				X	X	Х	SOC	Х	
Coagulation 	Х	X 				X	X	SOC	SOC	Х	
Comprehensive Metabolic Panel 	Х	X 				X	X	Х	SOC	Х	
Serum Creatinine 	X	X 				X	X	Х	X	Х	
Complement C3a & C5a		X	Х	X		X	X	Х			
Arterial Blood Gases  (includes PaO 2 , PaCO 2 , pH, HCO 3 )		SOC	SOC	SOC		SOC	SOC	SOC			
Ionized Calcium, Total Serum Calcium, Serum Albumin		X	Х	X		X	X	Х			
Activated Clotting Time (ACT) 		SOC	SOC	SOC		SOC	SOC				

### Table 4: Schedule of Laboratory Assessments

			Pos	t-surgical pe	Discharge	Follow Up					
Event	Screening 	Pre-procedure Day of surgery but before induction of anesthesia	Start of CPB (±5 min)	Hourly while on CPB (±5 min)	90 minutes after Start of CBP Start of Device # 2) (±5 min)	End CPB  Off pump and post protamine	Admission to post- surgical care unit (+ 1 h)	Post- surgical Days 1-3	Post- surgical Days 4-7 or discharge, whichever is sooner	Hospital Discharge	30-day Follow up (±5 days)
Inflammatory Mediators 		X	Х	Х	Х	Х	Х	Х			
Kidney Injury Marker- Plasma HMGB1, Cystatin C		Х					Х	Х			
Kidney Injury Markers (Urine NGAL, TIMP2 & IGBFP7		Х					Х	Х			
Plasma Free Hemoglobin (pfHb) 		X	Х	Х	Х	Х	Х				
Urine Output						X	X 	$X^6$	X 	Х	X

 Within 14 days of surgery.

 If Screening is completed on the day of surgery, duplicate pre-procedure assessments/procedures do not need to be repeated.

 Daily for each post-surgical day.

 Women of child-bearing age without permanent birth control will be evaluated with a urine or serum pregnancy test within 7 days prior to CPB procedure.

 Samples to be drawn from an arterial line during cardiopulmonary bypass procedure. (End CPB sample to be drawn by appropriate medical staff per institutional guidance (i.e., anesthesiologist or perfusionist) t after CytoSorb Device is stopped at end of CPB)

 Urine output will be recorded hourly for the first 48 hours even if the urinary catheter is removed before 48 h after surgery. After 48 hours, urine output will be measured every 3 hours while the catheter is in place. Once the catheter is removed, urine output shall be recorded every 8 hours for 7 days or through hospital discharge, whichever occurs first.

 Pre-procedure blood samples will be drawn prior to induction of anesthesia.

 Hematology includes: Hemoglobin, WBC w/differential, Platelets and Hematocrit. Coagulation panel includes (Activated Partial Thromboplastin Time (APTT), Prothrombin Time/International Normalized Ratio (PT/INR), and fibrinogen)

 Comprehensive metabolic panel must include sodium and total bilirubin.

 Only required as per site's standard of care.

 Inflammatory mediators panel includes Interleukin 2 (IL2), Interleukin 4 (IL4), Interleukin 5 (IL5), Interleukin 6 (IL6), Interleukin 10 (IL10), Interleukin 12 (IL12S), Interferon Gamma (INFG), Tumor Necrosis Factor alpha (TNFA)

 Values will be collected for the study as long as the patient is intubated on mechanical ventilatory support. If the patient is not intubated on mechanical ventilatory support, they are not required for the study.

 End of CPB sample is drawn by appropriate medical staff per institutional guidelines (i.e., anesthesiologist or perfusionist) after pump shut off, per institution SOC for drawing coagulation panel post administration of Protamine.

 All creatinine values for assessment of AKI will be taken from local lab draws (CMP). At time of lab sample preparations, a backup creatinine sample will be drawn and prepared and sent to Central Laboratory for archiving only. In event of missed Creatinine value, the archive sample will be run by Central Lab.

### 8.8 Safety/Device Assessment

### 8.8.1 Adverse Events

Throughout the study, the Investigator or designee will determine adverse event (AE) occurrences. An adverse event is any untoward medical occurrence (signs, symptoms, abnormal laboratory findings) in a subject regardless of relationship to the device or procedure. Each adverse event is considered to be either anticipated or unanticipated as described below. AEs occurring after the initiation of treatment (start of CPB) are considered to be treatment emergent. The site is required to report the classes of Adverse Events that occur in the study, described below.

Any AEs and remedial action required will be recorded in the patient's source data. The nature, time of onset, duration, and severity will be documented, together with an Investigator's (or designee's) opinion of the relationship to investigational device. Since the incidence and severity of AKI, as defined by KDIGO clinical practice guidelines, are the primary endpoints of the study, the presence of AKI should not be reported as an AE in the trial.

If an AE occurs, appropriate diagnostic and therapeutic measures are to be taken. Follow-up evaluations of the patient are to be performed until the patient recovers or until the clinical Investigator considers the situation to be no longer clinically significant.

Adverse events are monitored and registered on the AE form of the eCRF at each visit. Whenever possible, a specific diagnosis should be entered as the AE term. Outcomes and severity of the AE are not to be recorded as the AE term. In absence of a specific diagnosis, an individual AE form has to be filled in for each sign or symptom. Changes from baseline laboratory values which are abnormal values and that are classified as clinically significant by the investigator must be recorded as AEs.

Persistent AEs will be entered once in the eCRF until they are resolved or if a new event has to be documented due to deterioration. These AEs will be carefully monitored. If an AE is still not resolved at the end of the investigation, this will be documented as ongoing.

For recurrent AEs (i.e., AEs of the same nature, but with a different date of onset), an individual AE form has to be completed for each of them.

Adverse events will be assessed for a relationship to each of the following and relationship classified as unrelated, possible, probable, definite or unknown:

**Investigational Device Related Adverse Event:** An adverse event which, in the judgment of the Investigator, results as a consequence of the investigational device.

**Surgical Procedure Related Adverse Event:** An adverse event which, in the judgment of the Investigator, results as a consequence of the subject's surgical procedure and is not specific to the investigational device used.

**Non-Investigational Device Related Adverse Event:** An adverse event which, in the judgment of the Investigator, it is reasonable to believe that the event is associated with an accessory device used during the surgical procedure and is not specific to the investigational device use.

Grade 1	Mild:	Asymptomatic or mild symptoms; clinical or diagnostic observations only; intervention not indicated.
Grade 2	Moderate:	Minimal, local or noninvasive intervention indicated; limiting age-appropriate instrumental Activities of Daily Living (ADL)*.
Grade 3	Severe:	Severe or medically significant but not immediately life-threatening; hospitalization or prolongation of hospitalization indicated; disabling; limiting self-care ADL**.
Grade 4***	Life- threatening:	Life-threatening consequences; urgent intervention indicated.
Grade 5***	Death:	Death related to AE

Adverse events will also be evaluated for severity based on the following definitions:

\*Instrumental ADL refer to preparing meals, shopping for groceries or clothes, using the telephone, managing money, etc. \*\*Self-care ADL refer to bathing, dressing and undressing, feeding self, using the toilet, taking medications, and not bedridden. \*\*\*Adverse events that are assigned a severity of life-threatening or death will be recorded as Serious Adverse Events.

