Study Population	
 
The population evaluated for effectiveness in the treatment group will consist of a primary sub-population and a secondary sub-population.
 
The primary sub-population includes all subjects enrolled and randomized to the treatment group who are undergoing valve replacement with another procedure (e.g., CABG and valve replacement) without Hypothermic Circulatory Arrest (HCA)
 
The secondary sub-population consists of all surgical subjects undergoing aortic reconstructions with or without other procedures (e.g., CABG, valve replacement) with HCA
 

Sample Size	40 investigational sites in the United States. A roll-in cohort of up to 80 additional subjects may be enrolled in the study and assigned to treatment with CytoSorb device.
Duration of participation for each patient	Primary, secondary, and exploratory endpoints will be evaluated on the day of cardiac surgery up to Day Seven (7) post-cardiac surgery or through hospital discharge, whichever occurs first. Subjects will be followed through 30-day follow-up visit to fully evaluate safety (AEs will be followed through study exit and device-related SAEs will be followed until a return to a stable state as determined by the investigator).
Patient treatment	Two devices, configured into a parallel circuit are placed between the oxygenator and the venous reservoir and run as a bypass shunt to the main blood flow in a standard heart-lung machine. The first device will be introduced at t=0 (start of CPB). The second device will be introduced at t=90 minutes after the start of CPB.
Study Objectives:	To evaluate the safety and performance of the CytoSorb ® device to decrease the incidence or severity of AKI in the first 48 hours after surgery when used intraoperatively with cardiopulmonary bypass (CPB) in subjects undergoing cardiac surgery. The study hypothesis is that, for patients at increased risk for AKI based upon use of the Cleveland Clinic Score for stratification of the risk of cardiac surgery associated AKI (CSA-AKI), the intra-operative usage of the CytoSorb ® device in addition to the standard of care in a bypass circuit during cardiopulmonary bypass will decrease the incidence or severity of AKI per the Kidney Disease Improving Global Outcomes (KDIGO) clinical practice guideline definition of acute kidney injury.

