AEs specifically related to the investigational device were infrequent (i.e., involving 2 [8.7%] subjects in the Treated arm with thrombocytopenia) and in both instances the subjects recovered without sequelae. The most frequent SAEs (occurring in  $\geq$  2 subjects in either treatment arm) were atrial fibrillation, thrombocytopenia, coagulopathy, anemia, anemia postoperative, pleural effusion, hypotension, malnutrition, and acute kidney injury. There were no appreciable differences in the frequency of SAEs between treatment arms.

Additionally, the Data Monitoring Committee (DMC) will be reviewing safety information on an ongoing basis, and this will also provide an additional level of risk mitigation.

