### 6.3 Study Outcomes

### 6.3.1 Primary Safety Endpoint

The primary safety endpoint of this trial is to evaluate the product safety profile through the assessment of device related adverse events during the study period.

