#### 6.3.4 Secondary Effectiveness Endpoint(s)

Secondary effectiveness endpoints include the following:

- Change from baseline (defined as the start of CPB) in pfHb assessed hourly for the duration of CPB and at the end of CPB;
- Change from baseline (defined as start of CPB) in Complement 3a (C3a) assessed hourly for the duration of CPB and at the end of CPB;
- Severity of AKI through hospital discharge or post-surgical Day 7, whichever is sooner
- Incidence of AKI through hospital discharge or post-surgical Day 7, whichever is sooner
- Change from baseline (defined as pre-procedure) in serum creatinine through hospital discharge or post-surgical Day 7, whichever is sooner;

Additionally, the following pharmacoeconomic endpoints are included:

- Duration of hospital stay, post-surgery
- Duration of ICU stay, post-surgery
- Duration of renal replacement therapy, post-surgery
- Duration of vasopressor use, post-surgery
- Duration of ventilator use, post-surgery

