### 8.1 AKI Definition, Severity Grading, and Duration

Acute kidney injury (AKI) is defined in the KDIGO guidelines as meeting any of the following:

• Increase in serum creatinine by  $\geq 0.3 \text{ mg/dL}$  ( $\geq 26.5 \mu \text{mol/L}$ ) within 48 h or;

- Increase in serum creatinine to ≥1.5 times baseline, which is known or presumed to have occurred within the prior 7 days or;
- Urine volume < 0.5 ml/kg/h for 6 hours

For the purposes of this study, the 48-h referenced in the first part of the definition will be the first 48 h following admission to the ICU (or equivalent post-surgical placement). Serum creatinine and urine volume (urine output) will be recorded through post-surgical Day 7 or hospital discharge, whichever comes sooner.

Staging of AKI for severity assessment will use the criteria summarized in the table below. Staging of AKI may be based on either change in serum creatinine OR changes in urine output.

Stage	Serum Creatinine	Urine Output
1	1.5 to 1.9-times baseline or ≥0.3 mg/dL (≥26.5 µmol/L) increase	< 0.5 mL/kg/h for 6-12 h
2	2.0-2.9 times baseline	$< 0.5 \text{ mL/kg/h for} \ge 12 \text{ h}$
3	3.0 times baseline or SCr ≥4.0 mg/dl (≥353.6 µmol/L) or Initiation of renal replacement therapy	< 0.3 mL/kg/h for $\ge$ 24 h or Anuria for $\ge$ 12 h

Duration of AKI will be assessed through post-surgical Day 7 or hospital discharge whichever comes sooner. Duration of AKI is measured as the number of days from the point where the patient meets the criteria of AKI per the KDIGO definition until the point where the definition is no longer met.

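### The rule that AKI is not an adverse event has no end date, so AKI starting after Day 7 or discharge is captured unreliably; the SAP also drops both Day 7/discharge AKI endpoints without naming them

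*Protocol*

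**What the plan says.** Protocol 8.8.1 gives AKI's status as the primary endpoint as its reason and then instructs that "the presence of AKI should not be reported as an AE in the trial". No period is attached.

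The AKI endpoints and their data are bounded. The primary endpoint (6.3.2) covers the first 48 hours. Section 6.3.4 adds two secondary endpoints, severity of AKI and "Incidence of AKI through hospital discharge or post-surgical Day 7, whichever is sooner". Section 8.1 sets the collection period: "Serum creatinine and urine volume (urine output) will be recorded through post-surgical Day 7 or hospital discharge, whichever comes sooner".

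Safety follow-up is longer. The Synopsis states that "AEs will be followed through study exit", and study exit follows the 30-day contact. The procedure-related adverse event endpoint (6.3.3) and Clinical Events Committee review (9.1) also run to 30 days. The primary safety endpoint (6.3.1) is to "evaluate the product safety profile through the assessment of device related adverse events during the study period". On the last contact, 8.7 says: "The subjects will be contacted via telephone at 30 days post-cardiac surgery for assessment of the following since hospital discharge". It lists transfusions and adverse events, with no renal item.

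The SAP stages AKI at 48 hours (6.7.1.1, and the subgroup outcome in 6.9). Its secondary efficacy section (6.7.2) contains only health-economic parameters.

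**The concern.** An exemption from adverse event reporting is sound when the same events are captured and analysed as an endpoint. Here the exemption, as worded, outlasts the endpoint. Once endpoint collection has ended, AKI is no longer measured on schedule, and a site that follows 8.8.1 literally does not report it either.

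The event matters for this device. It is being tested for kidney protection, and section 5.2 lists hemolysis among its residual risks. Section 5.3 names the most frequent serious adverse events of the sponsor's earlier trial, and the list ends with "anemia postoperative, pleural effusion, hypotension, malnutrition, and acute kidney injury". If later-onset AKI is missing from the adverse event and device-related tables, a reader cannot tell whether it did not occur or was not reported.

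**Working it through.** The plan states no figure on this point, so the check sets the passages side by side and counts days.

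**1. Windows.**

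| Item | Ends | Source |
|---|---|---|
| Primary AKI endpoint | 48 hours | Protocol 6.3.2 |
| Two secondary AKI endpoints | Day 7 or earlier discharge | Protocol 6.3.4 |
| Scheduled creatinine and urine output | Day 7 or earlier discharge | Protocol 8.1 |
| AKI exemption from AE reporting | not stated | Protocol 8.8.1 |
| AE follow-up | Day 30 (±5 days) | Synopsis; Table 3 |
| Procedure-related AE endpoint; committee review | Day 30 | Protocol 6.3.3; 9.1 |

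**2. Length of the gap.** Days with AE follow-up but no scheduled daily AKI data = last follow-up day − last collection day.
- Collection to Day 7, contact on Day 30: 30 − 7 = 23 days (Days 8 to 30).
- Contact at the edges of its window: 25 − 7 = 18 days, or 35 − 7 = 28 days.
- Discharge on Day 5 (assumed for illustration), contact on Day 30: 30 − 5 = 25 days.

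These are calendar days, not patients or events.

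**3. What a site is told to do with AKI in the gap.**
- 8.8.1, exemption: do not report it.
- 8.8.1, laboratory rule: a clinically significant abnormal change from baseline must be recorded as an adverse event, with no exception for creatinine.
- 8.8.3: kidney injury is among the anticipated events.
- 8.8.2 with 8.9.1: an untoward occurrence meeting a seriousness criterion is an SAE, to be reported within 24 hours, with no exception for AKI.

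No passage ranks these rules or says when the exemption ends. Two sites could handle the same case differently, and each could cite the protocol.

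**4. Backstops.** A patient still in hospital after Day 7 has one discharge assessment (8.6.4), which includes creatinine, urine output and "Record need for renal replacement". It is a single look and cannot see onset after discharge. The Day 30 call asks about adverse events, but that item is subject to the same exemption. Table 4 appears to mark urine output at Day 30, against its own footnote 6 and a telephone contact. The columns may be misaligned, the mark adds no creatinine, and nothing here rests on it. The committee reviews only events that are reported.

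**5. SAP.** AKI endpoints to Day 7/discharge in Protocol 6.3.4: 2. Carried into SAP 6.7.2: 0. What remains beyond 48 hours is creatinine by visit with shift tables (6.8.2.5) and renal replacement summaries (6.7.2.1, 6.8.5). Neither gives AKI incidence or stage.

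**The case against.** The best defence is that the exemption's own rationale implies a limit, that other rules already route later AKI into the safety data, and that the study has stopped. Each part has weight.

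- *Implied limit.* The rationale does favour a bounded reading, but the text does not say whether the bound is 48 hours or Day 7/discharge.
- *Other routes.* A reader might infer that late AKI cannot enter the primary safety endpoint. The documents do not support that. Under the laboratory rule, a clinically significant creatinine rise gets an adverse event form and a device-relatedness rating. The UADE definition (8.8.4) also has no AKI exception. What stands is that the instructions conflict.
- *SAE status.* A reader might take the severity-table note in 8.8.1 to mean that only graded adverse events can become SAEs, which would shut AKI out. The note adds a route for life-threatening and fatal events. It does not restrict 8.8.2 or 8.9.1.
- *Days 2 to 7.* A reader might count everything after 48 hours as uncovered. Creatinine and urine output are collected to Day 7/discharge, and creatinine is summarised by visit. In that period the weakness is the missing SAP analysis, not missing data.
- *Earlier trial.* No comparison of safety tables with it is planned, and section 5.3 gives no onset times. It shows that AKI was a frequent SAE and says nothing about late onset.
- *Early stopping.* SAP 1 and 4.1 warn that analyses may differ from the protocol, and the SAP issue does not arise from the exemption. Both facts lower the weight. The SAP still governs the final report, and it does not name the two AKI endpoints as dropped.

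**Conclusion.** The concern holds in this form: capture of later-onset AKI is unreliable, not impossible. With collection to Day 7, the period at risk is Days 8 to 30 (23 days), and it is longer after earlier discharge. Sites have conflicting instructions throughout it, so no conclusion can be drawn from AKI's absence in the adverse event and device-related tables. The 48-hour randomized comparison of early AKI is not affected.

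Separately, two protocol AKI endpoints disappear from the SAP without being named, although their data are collected.

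The conclusion assumes that sites had no further written guidance on reporting AKI; the documents describe none. It makes no claim about how many patients had late AKI, which cannot be derived. Severity is minor to moderate.

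**What to change.** 1. **SAP.** Restore the analysis of AKI incidence and severity through Day 7/discharge, using the creatinine and urine output already collected.
2. **Stopped study (151 of 420 enrolled, including roll-ins).** Query sites for later-onset AKI where records exist. Otherwise state in the report that AKI was exempt from adverse event reporting, so the adverse event tables and the primary safety endpoint do not reliably include it.
3. **Protocol, for any restart.** Limit the 8.8.1 exemption to AKI with onset inside the window analysed as an endpoint, and require later-onset AKI through Day 30 to be reported as an AE or SAE. Reconcile the exemption with the laboratory rule in 8.8.1, the anticipated-event list in 8.8.3 and the SAE rules in 8.8.2 and 8.9.1. State which rule governs endpoint AKI that meets an SAE criterion.

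The cost is one extra analysis, a site query or a limitation sentence, and, after a restart, a few more AE/SAE forms. Data obtained retrospectively may be incomplete, and the report should say so.
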